13.1	Emergency communication with study participants	80
14	Acronyms and abbreviations.....	81
15	Protocol version history	83
16	Document references (other than literature citations).....	84
17	References.....	86
Appendix A	Sample informed consent form	97
Appendix B	Approved birth control methods (for sample informed consent form)	120
Appendix C	Sample consent form for use of samples and information in other studies.....	121
Appendix D	Tables of procedures for sample informed consent form.....	126
Appendix E	Laboratory procedures—Schedule 1: Monitoring ATI.....	131
Appendix F	Laboratory procedures—Schedule 2: Monitoring ATI with viremia.....	135
Appendix G	Laboratory procedures—Schedule 3: Follow-up on ART	139
Appendix H	Procedures at CRS—Schedule 1: Monitoring ATI.....	141
Appendix I	Procedures at CRS—Schedule 2: Monitoring ATI with viremia.....	145
Appendix J	Procedures at CRS—Schedule 3: Follow-up on ART	147
Appendix K	Visit Windows.....	148
Appendix L	Protocol Signature Page	153

1 Protocol summary

- Full title: Antiretroviral analytical treatment interruption (ATI) to assess immunologic and virologic responses in participants who initiated ART in early HIV infection after having received VRC01 or placebo in HVTN 703/HPTN 081
- Short title: HVTN 805/HPTN 093
- Sponsor: NIAID Division of AIDS
- Conducted by: HIV Vaccine Trials Network (HVTN) and HIV Prevention Trials Network (HPTN)
- Protocol chairs: [name], MPH; [name]; [name], MSc
- Sample size: 16 - 61
- Study population: HVTN 703/HPTN 081 participants living with HIV who met criteria for transition to Schedule 2 or Schedule 3 in that trial
- Study design: An exploratory study of participants living with HIV undergoing an analytical treatment interruption after early initiation of antiretroviral therapy (ART) following HIV acquisition in HVTN 703/HPTN 081, where they received VRC01 or placebo infusions
- Study duration: Study duration is potentially indefinite for a participant maintaining extended viral control during ATI. Study duration for most participants is expected to be 13-18 months. The maximum anticipated duration for any participant is expected to be approximately 2½ to 3 years.
- Study products: None. Drugs for ART and for pre-exposure prophylaxis (PrEP) will not be provided by the study or paid for using sponsor funds. Access to external funding sources for PrEP and ART provision is available and is detailed in the HVTN 805/HPTN 093 Study Specific Procedures (SSP).
- Primary hypotheses: Individuals who initiated ART early in HIV infection in HVTN 703/HPTN 081 will suppress plasma viremia and maintain CD4+ T-cell counts longer during ATI than historical cohorts (ie, SPARTAC African and non-African cohorts described in Gossez et al (1) comprising individuals who initiated ART early in HIV infection without other interventions).

Individuals who initiated ART early in HIV infection and also received VRC01 within 8 weeks before or after acquiring HIV in HVTN 703/HPTN 081 will suppress plasma viremia and maintain CD4+ T-cell counts longer during ATI than those who initiated ART early in HIV infection and received placebo within 8 weeks before or after acquiring HIV in HVTN 703/HPTN 081.

ATI will be safe and well-tolerated in individuals who acquired HIV during their participation in HVTN 703/HPTN 081.

Primary objectives: To evaluate the effect of early ART initiation, with or without having received VRC01 in the immediate pre-HIV acquisition period and/or during early infection, on the time to meeting ART re-initiation criteria in participants undergoing ATI

To evaluate the safety of ATI among HVTN 805/HPTN 093 participants

Secondary hypotheses: Individuals who initiated ART early in HIV infection and also received VRC01 within 8 weeks before or after acquiring HIV in HVTN 703/HPTN 081 will have enhanced cellular and humoral responses compared with those who initiated ART early in HIV infection and received placebo within 8 weeks of acquiring HIV in HVTN 703/HPTN 081.

Individuals who initiated ART early in HIV infection and also received VRC01 within 8 weeks before or after acquiring HIV in HVTN 703/HPTN 081 will have more limited viral reservoirs, before and after ATI, than those who initiated ART early in HIV infection and received placebo within 8 weeks of acquiring HIV in HVTN 703/HPTN 081.

Secondary objectives: To evaluate the effect of early ART initiation, with or without having received VRC01 in the immediate pre-HIV acquisition period and/or during early infection, on the development of anti-HIV immune responses and on the potential association of those immune responses with time to meeting criteria for ART re-initiation in participants undergoing ATI

To evaluate the effect of early ART initiation, with or without having received VRC01 in the immediate pre-HIV

acquisition period and/or during early infection, on viral load in participants undergoing ATI

To evaluate the effect of early ART initiation, with or without having received VRC01 in the immediate pre-HIV acquisition period and/or during early infection, on HIV reservoir size before and after ATI, and whether HIV reservoir measurements are associated with time to meeting criteria for ART re-initiation in participants undergoing ATI

[figure not shown]
1.1 Précis

While plasma viremia rebounds rapidly in most chronically HIV-infected individuals upon cessation of therapy, early initiation of ART after HIV diagnosis has been associated with later ART-free virologic control in individuals known as “post-treatment controllers” (PTCs). Similarly, preclinical (eg, murine, nonhuman primate [NHP]) and clinical evidence suggest that the presence of broadly neutralizing anti-HIV-1 antibodies (bnAbs), even at a concentration, or with a neutralization sensitivity profile, insufficient to prevent HIV acquisition, may nevertheless modulate the autologous response to HIV infection in ways that help set the stage for later durable virologic control. There is also evidence suggesting that early ART initiation and the presence of bnAbs at the time of or soon after HIV infection may be capable of limiting the establishment of and decreasing the size of viral reservoirs. Whether and how these effects might act together to support durable viral control, and what biomarkers may predict such control, is unknown.

The Antibody Mediated Prevention (AMP) studies HVTN 704/HPTN 085 and HVTN 703/HPTN 081, phase 2b studies assessing the ability of the CD4 binding site bnAb VRC01 to prevent HIV-1 infection, provide a unique opportunity to assess the impact of these hypothesized effects. The AMP studies currently have the only cohort of HIV-1–infected individuals who were diagnosed soon after acquisition, who initiated ART relatively soon after diagnosis, and a subset of whom had bnAb present at or near the time of infection. A pause in antiretroviral treatment—that is, an ATI—is the only way to determine whether early ART initiation with and without VRC01 circulating around the time of HIV acquisition, results in blunted, delayed, or absent viral rebound following discontinuation of ART, or subsequent immune control of any rebound that may be observed. If such an impact is observed, ATI is also the best means of assessing mechanisms and identifying predictive biomarkers of that impact through assessment of innate, cellular, and humoral markers along with characterization of the viral reservoir. Extensive virologic, immunologic, and safety monitoring will be conducted, and the trial has been formulated for consistency with recent consensus guidelines on the design and conduct of ATI studies (2, 3), particularly with respect to risk mitigation.

The study schema is shown below.

1.2 Schema

	SCREEN	PRE-DISCONTINUE ART	SCHEDULE 1			SCHEDULE 2			PRE-REINITIATE ART	SCHEDULE 3		
			ATI WEEKS 0-8	ATI WEEKS 10-24	ATI WEEKS 28-52 ¹	ATI + Viremia WEEKS 0-8	ATI + Viremia WEEKS 10-36	ATI + Viremia WEEKS 40-52 ²		FOLLOW UP ON ART WEEKS 0-12	FOLLOW UP ON ART WEEKS 12-28	FOLLOW UP ON ART WEEKS 40-52
Plasma HIV RNA	✓	✓	WEEKLY	Q2 WEEKS	Q4 WEEKS	WEEKLY	Q2 WEEKS ³	Q4 WEEKS	✓	Q2 WEEKS	Q4 WEEKS	Q12 WEEKS
CD4+ & CD8+ T cell counts	✓	✓	Q2 WEEKS	Q4 WEEKS	Q8 WEEKS	Q2 WEEKS	Q4 WEEKS ⁴	Q8 WEEKS	✓	Q4 WEEKS	Q8 WEEKS	Q12 WEEKS
Hematology & Chemistries	✓	✓	Q4 WEEKS		Q8 WEEKS	Q4 WEEKS		Q8 WEEKS	—	Q4 WEEKS	Q12 WEEKS	Q12 WEEKS

¹ QUARTERLY FOLLOW-UP VISITS MAY CONTINUE BEYOND WEEK 52 FOR PARTICIPANTS WHO DO NOT MEET CRITERIA FOR TRANSITION TO SCHEDULE 2.

² QUARTERLY FOLLOW-UP VISITS MAY CONTINUE BEYOND WEEK 52 FOR PARTICIPANTS WHO DO NOT MEET CRITERIA FOR ART RE-INITIATION.

³ OR WEEKLY FOR WEEKS 10-24, IF VL ≥ 200 copies/mL

⁴ OR Q2 WEEKS FOR WEEKS 10-24 IF VL ≥ 200 copies/mL

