- History of AIDS-defining illness according to Centers for Disease Control and Prevention criteria
- History of CD4 nadir <200 cells per μL during chronic stages of infection
- Women who are pregnant or breastfeeding
- Advanced non-alcoholic fatty liver and advanced nonalcoholic steatohepatitis, if evidence for substantial fibrosis (fibrosis score $\geq F2$) or evidence of cirrhosis
- HIV-related kidney disease or moderate-to-severe decrease in estimated glomerular filtration rate ($<45\text{--}60$ mL/min/1.73 m²)
- Children younger than 2 years of age when the ATI is planned

Monitoring

- HIV RNA monitoring weekly for 12 weeks, then every other week
- CD4 count monitoring every two weeks
- Monitoring of clinical symptoms, in particular in people who started ART during the hyperacute HIV phase
- Monitoring of participants' psychosocial experiences

ART restart criteria

- If requested by the participant or their HIV health-care provider
- If participant becomes pregnant
- If ART is deemed medically necessary for non-HIV related causes
- Symptomatic HIV disease||
- Confirmed absolute CD4 value <350 cells per μL or CD4% $<15\%$ **
- HIV RNA ≥ 1000 copies per mL for 4 weeks††
- Absolute HIV RNA $>100\,000$ copies per mL††

Reducing risk of HIV transmission to sexual partners

- Offer pre-exposure prophylaxis and HIV testing referral information that trial participants can provide to their sexual partners

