2.6 Ethical considerations

In the last 2 decades of treatment interruption conduct, an ethical framework for the conduct of such studies has evolved. There is general agreement that the risks of treatment interruption must be minimized; the trial must provide valuable data to answer an important question; and there must be no other methods entailing less risk that could answer that question (109, 110).

While ethicists have noted that “in general, the risks of the ATI itself, when closely monitored, are considered to be low,” risk mitigation is an essential part of the design of any treatment interruption. Risk mitigation includes but is not limited to: adoption of appropriate eligibility criteria; efforts to enhance potential participant benefits; community engagement in the design and implementation of the trial; frequent participant monitoring, balanced with considerations of participant burden; and a sound informed consent process. The informed consent process should acknowledge the risks and the lack of anticipated individual benefits, the fact that treatment interruptions are not recommended in clinical care, and the fact that ART guidelines recommend lifelong treatment (109, 110).

Each of these recommendations has been adopted by the HVTN 805/HPTN 093 Protocol Team. The HVTN 805/HPTN 093 informed consent process and Sample Informed Consent Form (SICF) include all points noted above and include elements demonstrated to improve the quality of informed consent in not only HIV research but also other fields (see Section 12.1). Trial design, including eligibility and ART re-initiation criteria, ATI duration, and monitoring frequency, are modeled on the most recent consensus guidelines for treatment interruption design (see Figure 2-16 above) (2, 3). The HVTN 805/HPTN 093 Protocol Team will implement not only rigorous counseling for participants on reducing HIV transmission risk to their partners but also a program for PrEP provision to participants' partners while the participant is enrolled; HIV genotyping (not standard of care in many AMP regions, unless first-line ART options have been exhausted); and accelerated, physician-led ART (re-initiation) access for participants in regions where ART stock-outs, public nurse-led care, and a window of several weeks between meeting ART re-initiation criteria and ART initiation could pose challenges for participants.

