3.3.2 Transition from Schedule 1, *Monitoring ATI* to Schedule 3, *Follow-up on ART*

For participants on Schedule 1, *Monitoring ATI*, any of the following non-virologic criteria will trigger ART re-initiation and transition to Schedule 3, *Follow-up on ART*:

- Confirmed CD4+ T-cell count < 350 cells/mm³ (ie, on 2 consecutive samples)
- Any HIV-related syndrome (eg, ARS, an opportunistic infection)
- Pregnancy or breastfeeding
- ART re-initiation requested by participant
- ART re-initiation requested by primary HIV care provider or clinical research site (CRS) Investigator of Record (IoR) (eg, if deemed medically necessary)

A confirmatory sample should be drawn at the next visit (within approximately 1-2 weeks) following the first CD4+ T-cell count < 350 cells/mm³ (see HVTN 805/HPTN 093 SSP for details).

3.3.3 Transition from Schedule 2, *ATI monitoring with viremia*, to Schedule 3, *Follow-up on ART*

For participants on Schedule 2, *Monitoring ATI with viremia*, the following virologic criteria will trigger ART re-initiation and transition to Schedule 3, *Follow-up on ART*.

From the Week 0 visit to the Week 24 visit in Schedule 2:

- Viral load remains $\geq 1,000$ copies/mL for ≥ 4 consecutive weeks AND viral load has not dropped 0.5 log from the previous week

This ART re-initiation criterion applies irrespective of missed visits and must take account of VL results $\geq 1,000$ copies/mL experienced by a participant while on Schedule 1. Furthermore, assessing whether participants meet this criterion may require additional visits beyond those scheduled from Week 8 (Visit 48) to Week 24 (Visit 56) in Schedule 2. Ideally, these additional visits will be conducted weekly. These additional visits will be treated as interim visits (for more details, see the HVTN 805/HPTN 093 SSP).

After the Week 24 visit in Schedule 2, the ART re-initiation criterion is:

- Confirmed viral load ≥ 200 copies/mL (ie, on 2 consecutive samples).

A confirmatory sample should be drawn at the next visit (within approximately 1-2 weeks) following the first VL result ≥ 200 copies/mL (see HVTN 805/HPTN 093 SSP for details).

The above virologic ART re-initiation criteria are shown schematically in [Figure 3-1](#).

Figure 3-1 Virologic criteria for transition from Schedule 2 to Schedule 3 (ie, ART re-initiation)

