6.4 Interim visits

Confirmatory VL samples and confirmatory CD4+ T cell samples may be drawn at interim visits (see Sections 3.3.1, 3.3.2, and 3.3.3). At interim visits for this purpose, the following clinical procedures will be performed:

- Targeted physical exam
- Assessment of concomitant medications
- Intercurrent illness/adverse experiences (AEs)
- ART re-initiation assessment
- HIV transmission risk behavior assessment and counseling
- Social impact assessment

Additional procedures may be performed at the discretion of the clinician.

For additional information on interim visits, including interim visits for other reasons, see the HVTN 805/HPTN 093 SSP.

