¹⁰ Additional weekly viral load monitoring may be required between weeks 8 and 24; after week 24, a confirmatory sample should be drawn at the next visit (within approximately 1-2 weeks) following the first VL result ≥ 200 copies/mL (see Protocol Section 3.3.3 and HVTN 805/HPTN 093 SSP for details). The 56-day blood draw limit does not include up to 10mL blood collected per visit for this additional monitoring; however, the 56-day limit is not exceeded at any visit by these collections.

¹¹ A confirmatory sample should be drawn at the next visit (within approximately 1-2 weeks) following the first CD4+ T-cell count < 350 cells/mm³ (see Protocol Section 3.3.3 and HVTN 805/HPTN 093 SSP for details).

¹² For persons capable of becoming pregnant, pregnancy test may be performed on urine or blood specimens.

¹³ At an early termination visit for a withdrawn or terminated participant (see Protocol Section 6.5), blood should be drawn as shown for Extended follow-up visit type A (see HVTN 805/HPTN 093 SSP for more information).

w = SST blood collected for syphilis testing will also cover specimen needs for HBsAg and anti-HCV screening testing. Hormone panel is defined in Protocol Sections 6.1 (Schedule 1: Monitoring ATI) and 6.2 (Schedule 2: Monitoring ATI with viremia).

y = SST blood collected for neutralizing antibody will also cover specimen needs for FcR-mediated effector functions; no separate blood draw is needed.

z = PBMC blood collected for ICS will also cover specimen needs for phenotyping; no separate blood draw is needed.

Laboratory procedures—Schedule 2: Monitoring ATI with viremia (continued)

Procedure	Ship to ¹	Assay location ^{1,2}	Tube Type ³	Tube size (vol. capacity) ³	Visit:	56	57	58	59	60	61	62	63	64	65	66	Visit Type A ^{8,13}	Visit type B ⁹	Total
					Days on ATI with viremia	D168	D182	D196	D210	D224	D238	D252	D280	D308	D336	D364			
					Weeks on ATI with viremia	W24	W26	W28	W30	W32	W34	W36	W40	W44	W48	W52			
BLOOD COLLECTION																			
Screening or diagnostic assays																			
HIV PCR viral load ¹⁰	Local labs	Local labs	EDTA	6mL	6	6	6	6	6	6	6	6	6	6	6	6	6	6	174
CD4+/CD8+ T-cell count ¹¹	Local labs	Local labs	EDTA	4mL	4	—	4	—	4	—	4	—	4	—	4	—	4	4	64
Safety labs																			
Hgb / ANC / PLT	Local labs	Local labs	EDTA	4mL	4	—	4	—	4	—	4	—	4	—	4	—	4	4	56
ALT / direct bilirubin / eGFR	Local labs	Local labs	SST	5mL	5	—	5	—	5	—	5	—	5	—	5	—	5	5	70
Syphilis ⁷	Local labs	Local labs	SST	5mL	5	—	5	—	5	—	5	—	5	—	5	—	5	5	80

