² HVTN Laboratories include: Fred Hutchinson Cancer Research Center (Seattle, Washington, USA); Duke University Medical Center (Durham, North Carolina, USA); South African Immunology Laboratory-National Institute for Communicable Diseases (SAIL-NICD, Johannesburg, South Africa); University of Cape Town (Cape Town, South Africa); Cape Town HVTN Immunology Laboratory (CHIL, Cape Town, South Africa).

Non-HVTN laboratories: TBD.

³ Local labs may assign appropriate alternative tube types for locally performed tests.

⁴ FcR-mediated effector function assays may include ADCC, virion capture, and phagocytosis assays.

⁵ 56-day totals do not include visit totals from Schedule 1 or 2. See HVTN 805/HPTN 093 SSP for details on prioritizing collections to avoid exceeding the 56-day limit.

⁶ Chlamydia/gonorrhea testing will be done on EITHER urine OR a cervical/vaginal swab; Trichomonas testing will be done on cervical/vaginal swab. In addition to STI testing at the marked visits, STI testing may occur at any visit if clinically indicated. In addition to the listed specimen types (ie., cervical/vaginal swabs), chlamydia/gonorrhea testing may occur on rectal swabs if clinically indicated (see HVTN 805/HPTN 093 SSP for details).

⁷ Samples for visit 80 should be collected after ART re-initiation criteria have been met, but prior to ART re-initiation.

⁸ HIV antiretroviral resistance testing will be performed only if indicated by viral load results (see HVTN 805/HPTN 093 SSP).

⁹ In addition to syphilis testing at the marked visits, syphilis testing may occur at any visit if clinically indicated.

¹⁰ Pregnancy testing is not required if viral load has returned to undetectable.

¹¹ For persons capable of becoming pregnant, pregnancy test may be performed on urine or blood specimens.

¹² At an early termination visit for a withdrawn or terminated participant (see Protocol Section 6.5), blood should be drawn as shown for Visit 91 (see HVTN 805/HPTN 093 SSP for more information).

¹³ Syphilis, chlamydia and gonorrhea testing is not required at this visit if viral load has returned to undetectable.

y = SST blood collected for neutralizing antibody will also cover specimen needs for FcR-mediated effector functions; no separate blood draw is needed.

z = PBMC blood collected for ICS will also cover specimen needs for phenotyping; no separate blood draw is needed.

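### The schema requires CD4 counts every 2 weeks for viremic participants in Schedule 2 weeks 10-24, but the Appendix F laboratory table schedules them only every 4 weeks

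*Protocol*

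**What the plan says.** **Schema.** Protocol 1.2 gives CD4 every 4 weeks for Schedule 2 weeks 10-36, and footnote 4 adds "OR Q2 WEEKS FOR WEEKS 10-24 IF VL ≥ 200 copies/mL". SAP 3.2 reprints the same footnote. Footnote 3 is the parallel rule for viral load: weekly in weeks 10-24 under the same condition.

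**Where sites are sent.** Protocol 6.2 lists CD4 counts among the Schedule 2 procedures and refers to Appendices F and I for the timepoints.

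**Appendix F.** In weeks 10-24 the CD4 row has a 4 mL tube at weeks 12, 16, 20 and 24 only. Two footnotes are relevant:
- Footnote 10, on the viral load row, provides for extra weekly viral load between weeks 8 and 24. It adds "The 56-day blood draw limit does not include up to 10mL blood collected per visit for this additional monitoring".
- Footnote 11 is the only footnote on the CD4 row. It covers confirmation of a low count: "A confirmatory sample should be drawn at the next visit (within approximately 1-2 weeks) following the first CD4+ T-cell count" falls below 350.

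**Other sections.** Protocol 3.3.3, on the virologic restart rule, says that "assessing whether participants meet this criterion may require additional visits beyond those scheduled from Week 8". Section 6.4 says "Confirmatory VL samples and confirmatory CD4+ T cell samples may be drawn at interim visits". Neither sets a routine CD4 frequency.

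**Stated basis for monitoring.** The consensus panel reproduced in Section 2.4 recommends "CD4 count monitoring every two weeks". Section 2.6 says that features including "monitoring frequency, are modeled on the most recent consensus guidelines for treatment interruption design".

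**The concern.** The viral load rule in schema footnote 3 reaches the laboratory table through footnote 10 and is reflected in Section 3.3.3. The matching CD4 rule reaches neither. The laboratory tables do use footnotes for sampling that depends on viral load. Appendix G footnote 13, for example, reads "Syphilis, chlamydia and gonorrhea testing is not required at this visit if viral load has returned to undetectable". The omission is therefore not a matter of table style.

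Confirmed CD4 below 350 requires ART to be restarted, and it is one of the criteria that define the time-to-event primary endpoint. Appendix I schedules an ART re-initiation assessment at weeks 10, 14, 18 and 22, and under Appendix F no CD4 is drawn at those visits.

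The gap matters most for participants who stay viremic without meeting the virologic restart rule through week 24. These are participants with viral load between 200 and 999, or at 1,000 or more with falls of 0.5 log. For them CD4 is the main laboratory trigger. Footnote 4 is also the only scheduling text that gives viremic participants in weeks 10-24 the 2-weekly CD4 frequency of the consensus panel.

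**Working it through.** **1. Is the table read correctly?** The columns are easy to misread, so the reading was tested against the printed totals.

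- CD4 row: weeks 0, 2, 4, 6, 8 (5 draws); weeks 12, 16, 20, 24 (4); weeks 28, 32, 36, 44, 52 (5); extended visits A and B (2). That is 16 draws × 4 mL = 64 mL, the printed row total.
- Viral load row: 27 scheduled visits + 2 extended visits = 29 draws × 6 mL = 174 mL, the printed row total.
- Full visit: 6 + 4 + 4 + 5 + 5 + 2 + 42.5 + 8.5 + 10 + 17 = 104 mL, the printed total at weeks 12, 16, 20 and 24.
- Weeks 10, 14, 18 and 22: the printed visit total is 6 mL, which is the viral load tube alone.
- 56-day totals: summing visit totals from week w − 8 to week w reproduces every printed value from week 0 to week 52. For example, week 16 is 104 + 6 + 104 + 6 + 104 = 324.

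The table therefore has no CD4 draw at weeks 10, 14, 18 or 22.

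**2. Draws in weeks 10-24 when viral load is 200 or more**

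| Source | Weeks | Draws |
|---|---|---|
| Schema footnote 4 | 10, 12, 14, 16, 18, 20, 22, 24 | 8 |
| Appendix F | 12, 16, 20, 24 | 4 |

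The four missing draws come to 4 × 4 = 16 mL.

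**3. Delay in finding a first low count.** Assume visits on target days, a sustained fall below 350, and an onset uniform over weeks 8-24.

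- 4-weekly sampling: the wait is uniform on 0-28 days, mean 14 days.
- 2-weekly sampling: the wait is uniform on 0-14 days, mean 7 days.
- Difference: 14 days if the fall comes in the first half of a 4-week interval, 0 days if it comes in the second half. The mean is 0.5 × 14 + 0.5 × 0 = 7 days and the maximum is 14 days.

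The confirmatory sample follows the same rule under both schedules, so it does not change the difference.

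**4. Blood volume if the four draws are added**

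| Week | Printed 56-day total (mL) | Plus 2-weekly CD4 | Plus weekly viral load as well |
|---|---|---|---|
| 12 | 313 | 313 + 4 = 317 | 317 + 2 × 6 = 329 |
| 16, 20, 24 | 324 | 324 + 2 × 4 = 332 | 332 + 4 × 6 = 356 |
| 28 | 324 | 324 + 4 = 328 | 328 + 2 × 6 = 340 |

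All are below the table's own peak of 369.5 mL at week 8. The CD4 row total would rise from 64 to 80 mL.

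**The case against.** The strongest reply is that the rule is already in the protocol. Footnote 4 is current text, Appendix F prints the unconditional schedule and agrees with the schema's 4-weekly cell, and nothing says the appendix overrides the schema. On this view it is an incomplete cross-reference. But Section 6.2 directs sites to Appendix F for timepoints, and a reader of that table is not told to draw CD4 at weeks 10, 14, 18 or 22. If the schema governs, the table still needs correcting.

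Footnote 10's allowance of 10 mL per visit equals one 6 mL viral load tube plus one 4 mL CD4 tube, so CD4 was probably intended. That stands as evidence of intent. The footnote names only viral load, however, and gives no CD4 frequency. Section 2.4 also lists biweekly monitoring that includes CD4 among the safety features, but as general background not tied to these weeks.

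The Study Specific Procedures may carry the rule. They are not available, so this cannot be excluded. An entry there would protect participants but would leave the protocol inconsistent with itself.

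The points about weight stand in part:
- Entry requires CD4 of at least 450.
- Sustained viral load of 1,000 or more without a 0.5-log fall already leads to restart. So do HIV-related syndromes and requests from the participant, care provider or investigator.
- The Protocol Safety Review Team reviews CD4 and viral load twice a month.
- A restart assessment without a same-day CD4 is planned at Schedule 2 weeks 1, 3, 5 and 7, so it is not a fault in itself.
- The protocol openly uses 4-weekly CD4 in Schedule 1 weeks 10-24, so it does not follow the consensus panel everywhere.

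These limit the harm. They do not supply the missing instruction.

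**Conclusion.** The concern holds. For viremic participants in Schedule 2 weeks 10-24, the schema requires twice as many CD4 draws as Appendix F schedules (8 versus 4), and no other section or footnote closes the gap. The reading of the table is secure because it reproduces the printed row, visit and 56-day totals.

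The consequence is modest: a first CD4 below 350 found up to 14 days later, 7 days on average under the assumptions in step 3. It applies only where a site follows the table and the Study Specific Procedures do not supply the rule. The documents do not give the number of participants affected. No power, alpha or analysis method changes. Because the gap falls on a protective restart criterion that is also part of the primary endpoint, and is cheap to close, it should be corrected.

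**What to change.** Add a footnote to the CD4 row of Appendix F: in Schedule 2 weeks 10-24, if viral load is 200 copies/mL or more, CD4 is also drawn at weeks 10, 14, 18 and 22. Name CD4 beside viral load in footnote 10, so that its 10 mL allowance matches its wording. A matching line in Section 3.3.3 would help but is optional, since that section mainly sets restart criteria.

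The cost is a wording change plus up to four 4 mL tubes per viremic participant, all at visits already scheduled. The visit totals at those four weeks rise from 6 to 10 mL. The highest affected 56-day total is 332 mL, or 356 mL with weekly viral load, against the table's existing peak of 369.5 mL.
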